#### **Ethical statement Ethical principles**

The study should be carried out in accordance with Helsinki declaration proposed by World Medical Association and subsequent amendments and approved by the Independent Ethics Committee (IEC) before implementation.

#### Information and informed consent

- All the patients who agree to participate should be asked to sign the informed consent form to prove their approval for participation in this study. The informed consent form must be signed and dated personally by the patients and investigators.
- ➤ Before obtaining the informed consent, the investigators must provide sufficient information to the patients who are potential participants in this study:
- The investigators should orally inform the patients of all the relevant circumstances of this study;
- The information provided to patients must be fully and easily understood by non-professionals, so that they can make a decision according to their own willingness based on their full understanding of this study;
- Additionally, the patients voluntarily participate in the study, and are free to quit from the study at any time, without any reasons. The subsequent treatment of patients is not under the influence of unwilling to participate or quitting from the study.
- ➤ All the patients who agree to participate should be asked to sign the Informed Consent Form (ICF) to prove their approval for participation in this study. The ICF must be

signed and dated personally by the patients and the investigators;

The signed ICF will be kept in the Data Center and must be safely kept for future review at any time throughout the study.

#### Withdrawal from the study

The main withdrawal criteria are as following:

- ➤ Changes in the patient's condition after inclusion, which suggests that the study protocol is unsuitable for the patient;
- Severe complications affecting the implementation of the study treatment;
- ➤ Patients who are confirmed to require emergency treatment due to other diseases after inclusion;
- >Treatment unmated with the study protocol;
- ➤ Patients who voluntarily quit or discontinue any examination, treatment and monitoring required by the study for personal reasons at any stage after inclusion in this study. The PI also has the right to withdraw patients from the study if he/she feels that the withdrawal is in the best interests of the patients.

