#### Responsibility of independent ethics committee

The responsibilities of independent ethics committee include: >Review of this study;

- ➤ Evaluate this study to determine if risks to which patients are exposed have been duly minimized and whether these risks are reasonable compared to expected benefits;
- ➤ Check the study protocol and relevant documents (patient information sheet, ICF, CRF, etc.) submitted by the Research Committee before beginning of the study;
- ➤ Provide the written proof of ethical review opinions, the written proof of the date of the review meeting, the written proof of the members presenting at the meeting and voting members, the written proof of recording of the reviewed versions of study protocol, ICF and other related documents, and if possible, a copy of the minutes, to the Research Committee. The study can begin only after obtaining the written proof of favorable opinions/approval of the IEC;
- Supervise the legitimacy of the process of informed consent;
- ➤ Ensure the safety of patients during the research process by examining the reported safety information. The

investigators should report to the IEC on any therapeutic complications which may affect the safety of patients. When complications that affect the patient safety occur, the IEC should inform PI to withdraw patients from the study and use any possible treatment to cure patients. If the PI decides not to withdraw patients from the study, he should provide a written proof of explanation to the IEC; >Review the reasonableness of the costs incurred by patients in the course of the study through a selective check for hospitalization expenses. When the patient has indications for off-label use of drugs, the IEC will receive the notice and the description of relevant situation from the investigators. The IEC should record the relevant records;

- ➤ Review the revisions of the study protocol, and any changes must be approved by the IEC before they are adopted. Unless the change is necessary to eliminate an immediate hazard to the patients, in which case the IEC should be informed as soon as possible;
- ➤ Review the progress of the study annually and the closeout report submitted by the Research Committee at the end of the trial.

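### Clinical reasons for stopping treatment are written as reasons for leaving the study, so patients likely to be at higher risk can drop out of the TA-TMA analysis before diagnosis

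*Combined protocol and SAP*

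**What the plan says.** The section Withdrawal from the study holds one list of what it calls the main criteria. Several concern the patient's clinical course or treatment:

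- "Severe complications affecting the implementation of the study treatment";
- a change in condition "which suggests that the study protocol is unsuitable for the patient";
- a need for urgent care for another illness;
- "Treatment unmated with the study protocol".

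The list also covers patients who quit or who "discontinue any examination, treatment and monitoring required by the study for personal reasons". It closes with discretion: "The PI also has the right to withdraw patients from the study", where this is judged best for them.

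The section Responsibility of independent ethics committee uses the same vocabulary: "When complications that affect the patient safety occur, the IEC should inform PI to withdraw patients from the study". The default can be declined: "If the PI decides not to withdraw patients from the study, he should provide a written proof of explanation to the IEC".

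Statistical methods names Kaplan-Meier estimation, the log-rank test, the software, two-sided testing and the 0.05 level. It states no analysis population and no rule for censoring. The primary outcome is the incidence of TA-TMA, with no time window. Nowhere in the available text is stopping study drug a separate status, and nothing provides for TA-TMA follow-up after withdrawal. Some front pages and the consent pages were not available, so a provision there cannot be excluded.

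**The concern.** Kaplan-Meier and log-rank assume that a censored patient has the same later risk as those still observed. Most of the listed triggers are deterioration, complications or departures from planned treatment. The Background describes TA-TMA as a severe complication of transplantation that arises from endothelial injury. It is a reasonable inference, though the documents put no figure on it, that patients with severe complications have a higher TA-TMA risk than the rest. If they leave observation before diagnosis, their later events are never counted and the estimate comes from a lower-risk remainder.

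Three things are at stake: an incidence that is too low, fewer events and so less power, and a result that depends on whether withdrawn patients are censored, excluded or kept, with nothing settled in advance. A patient withdrawn after a TA-TMA diagnosis is not affected under censoring, because the event is already counted.

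**Working it through.** **The plan's own figure.** The Protocol Summary gives 300 patients randomised 1:1. No power, TA-TMA rate, effect size or dropout rate is given, so 300 can be neither reproduced nor refuted. It is used here only for 300/2 = 150 per arm.

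**Width per patient lost (no risk model).** One patient lost before diagnosis leaves 1/150 = 0.67 points of that arm's incidence undetermined. If 10% of an arm were lost (an assumed rate), 15/150 = 10 points would be undetermined. This is a width, not a bias.

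**Illustration (every input assumed).**
- Day-100 TA-TMA incidence is 15%.
- A share c = 20% of patients has a complication at a time uniform on days 0 to 30. It multiplies the later TA-TMA hazard by k.
- A proportion w of these patients is withdrawn at that time and censored. With w = 0.5, about 10% of all patients are withdrawn.

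With base hazard λ per day, the event-free shares still observed at day t are:
- no complication so far: U(t) = [1 − c·min(t,30)/30]·exp(−λt)
- complicated and retained: V(t) = c(1−w)·(1/30)·∫ exp(−λu − kλ(t−u)) du, for u from 0 to min(t,30)

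The Kaplan-Meier limit at day 100 is 1 − exp(−∫ λ(U + kV)/(U + V) dt). Expected events in 300 patients are 300·∫ λ(U + kV) dt. λ is set so that w = 0 gives 15%; for k = 3 it is 0.00124.

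Results with no drug effect (15% in both arms, 45 events with full follow-up):

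| k | Kaplan-Meier, w = 0.25 | Kaplan-Meier, w = 0.5 | Events, w = 0.25 | Events, w = 0.5 |
|---|---|---|---|---|
| 1 | 15.0% | 15.0% | 43.1 | 41.2 |
| 3 | 14.3% | 13.5% | 41.0 | 37.0 |
| 5 | 13.9% | 12.6% | 39.8 | 34.6 |

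For true incidence of 10% to 20% and k of 2 to 5, the understatement runs from 0.3 points (10.0 − 9.71) to 3.0 points (20.0 − 17.01). Excluding withdrawn patients instead of censoring them gives 13.7% at k = 3, w = 0.5.

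**Power at an assumed hazard ratio of 0.5** (control 15%, equal withdrawal in both arms, 40,000 simulated trials, about ±0.5 points). With k = 3 and full follow-up, expected events are 150 × 0.150 + 150 × 0.079 = 22.5 + 11.8, about 34. This is not the 45 of the no-effect case above.

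| k | w = 0 | w = 0.25 | w = 0.5 |
|---|---|---|---|
| 1 | 50.2% | 48.7% | 47.3% |
| 3 | 49.7% | 45.9% | 42.9% |
| 5 | 47.6% | 43.7% | 39.0% |

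At k = 1 the loss is 50.2 − 47.3 = 2.9 points, from lost follow-up alone. At k = 3 it is 49.7 − 42.9 = 6.8 points.

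**Type I error** (40,000 simulated trials, about ±0.2 points):

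| Complicated patients withdrawn, by arm | k = 3 | k = 5 |
|---|---|---|
| 50% vs 50% | 5.1% | 5.0% |
| 40% vs 60% | 5.3% | 5.6% |
| 30% vs 70% | 6.1% | 7.8% |

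At k = 3 the false difference in incidence is 13.82 − 13.16 = 0.7 points at 40% vs 60%, and 14.13 − 12.81 = 1.3 points at 30% vs 70%.

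**The case against.** **The withdrawal section never says that observation stops.** This stands. The plan also intends to estimate overall survival, event-free survival, recurrence and transplant-related mortality. These imply observation beyond the end of study drug at day 30, so the centre may in practice follow everyone. But nothing says that withdrawn patients are included, and leaving the study is ordinarily taken to end study observation. The finding is therefore about the plain reading of an unspecified rule, not a stated instruction to stop collecting data.

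**The ethics committee text is weaker support.** This also stands. It sets out a safety duty, not data handling, and it lets the investigator keep the patient in. A patient's freedom to quit is an ordinary consent right. The point rests on the clinical and off-protocol criteria, the investigator's discretion, and the silence of Statistical methods.

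**The size comes from assumptions.** This stands too. With k = 1 there is no bias in the estimate, and a moderate imbalance by arm barely moves the type I error.

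**A stronger reading is tempting: that the comparison of NAC with placebo is biased, or that false positives are inflated.** The documents do not support it. With equal withdrawal the test stays at about 5%, and no difference by arm is documented. Methodology calls the trial open-label, while Intervention describes identical-looking placebo tablets. Those statements need reconciling, but until they are, neither can be used to argue that withdrawal would or would not depend on arm.

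**Conclusion.** The concern holds as an exposure and should be fixed. As written, clinical and treatment-related reasons take a patient out of the study, nothing available keeps that patient under TA-TMA observation, and the planned methods would treat the loss as unrelated to risk. If withdrawal is positively related to TA-TMA risk and ends observation, incidence is understated and events and power fall.

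The omission is certain; its effect is not. The documents give no TA-TMA, complication or withdrawal rate, so the only figure free of a risk model is 0.67 points of undetermined incidence per patient lost in an arm. With k = 3 and half of complicated patients withdrawn, the assumed inputs give about 13.5% instead of 15%, about 37 events instead of 45 under no drug effect, and power of about 43% instead of 50% at a hazard ratio of 0.5.

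A reader might also infer a net direction for the reported incidence. None is claimed: if deaths are censored as well, Kaplan-Meier is pushed upward.

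**What to change.** Leave the clinical reasons for stopping, the investigator's discretion and the ethics committee's safety role unchanged.

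1. Reword Withdrawal from the study, and the ethics committee section to match, so that meeting a criterion does not end outcome follow-up. Follow every randomised patient for TA-TMA, relapse and survival, over the same window in both arms, unless the patient withdraws consent for follow-up.
2. State in Statistical methods that the primary analysis includes all randomised patients in their assigned arm, and that being off study drug is not a reason for censoring. Apart from the end of the common window, censor only at loss to follow-up or withdrawal of that consent.
3. Report withdrawals by arm, time and reason. Include a sensitivity analysis, such as a tipping-point analysis, for patients still lost, because censoring them still assumes that their loss is uninformative.

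The length of the window and the handling of death before TA-TMA are separate points.

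The cost is a protocol change, for which "any changes must be approved by the IEC before they are adopted", possibly new consent wording, some chart follow-up at the single centre, and some dilution of effect from patients off study drug. The analysis rules can still be set before the data are analysed, but outcomes not collected after withdrawal may not be recoverable.

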#### Identity and privacy of patients

After obtaining an ICF, each enrolled patient is assigned a subject number (allocation number). This number will represent the identity of the patient during the study and for the retrieving of dedicated clinical research database;

- ➤ Throughout the study, several measures will be taken to minimize any breaches of personal information, including:
- Only the PI and co-investigators will be able to link to the research data of the patients to themselves through the identifiable table after authorization;
- Collection, transmission, handling and storage of the study data must comply with the data protection and privacy regulations.

#### Responsibility of independent ethics committee

The responsibilities of independent ethics committee include: >Review of this study;

- ➤ Evaluate this study to determine if risks to which patients are exposed have been duly minimized and whether these risks are reasonable compared to expected benefits;
- ➤ Check the study protocol and relevant documents (patient information sheet, ICF, CRF, etc.) submitted by the Research Committee before beginning of the study;
- ➤ Provide the written proof of ethical review opinions, the written proof of the date of the review meeting, the written proof of the members presenting at the meeting and voting members, the written proof of recording of the reviewed versions of study protocol, ICF and other related documents, and if possible, a copy of the minutes, to the Research Committee. The study can begin only after obtaining the written proof of favorable opinions/approval of the IEC;
- Supervise the legitimacy of the process of informed consent;
- ➤ Ensure the safety of patients during the research process by examining the reported safety information. The

investigators should report to the IEC on any therapeutic complications which may affect the safety of patients. When complications that affect the patient safety occur, the IEC should inform PI to withdraw patients from the study and use any possible treatment to cure patients. If the PI decides not to withdraw patients from the study, he should provide a written proof of explanation to the IEC; >Review the reasonableness of the costs incurred by patients in the course of the study through a selective check for hospitalization expenses. When the patient has indications for off-label use of drugs, the IEC will receive the notice and the description of relevant situation from the investigators. The IEC should record the relevant records;

- ➤ Review the revisions of the study protocol, and any changes must be approved by the IEC before they are adopted. Unless the change is necessary to eliminate an immediate hazard to the patients, in which case the IEC should be informed as soon as possible;
- ➤ Review the progress of the study annually and the closeout report submitted by the Research Committee at the end of the trial.

# Responsibility of investigator

The responsibilities of investigators are as follows:

- ➤Investigators, participated in the clinical trial, should be obtained certificate for assistant practicing doctor, resigned and attended the training of the GCP guidelines and the correlation of laws and regulations, possessed specialty, qualification and ability in clinical trial.
- ➤ Subjects are adequately recruited by the investigator during required time according to the clinical trial, and

operation capacity and possibility to be qualified the item should be evaluated by the previous working experience.

Investigators are familiar with clinical trial protocols and execute instruction strictly according to the protocols and case report form.

➤ In all adverse events, subjects must be taken appropriate therapies and made a contact with the investigator as soon as possible. Investigators will take responsibilities of relevant medical decision of clinical trial to ensure subjects that is taken adequate medical treatment.

Any information on the case report form possesses original data, to ensure the case history and case report form filled in truly, accurately, completely, timely, regularly and legally.

Subjects will be illustrated the relevant situation where the clinical trial is fully consent by Ethics Committee. The informed consent will be acquired and, during the process, it must meet the specification.

Supervision and inspection will be received by supervisor and inspector assigned by sponsor to ensure the quality of clinical trial.

Any advices and suggestions focused on the study protocols might be submit to the principal institution of clinical research, and made a discussion with sponsors to decide whether adopting the above advice or suggestions, during the clinical trial.

#### **Publications**

➤ All the data collected during this study are the property of the study sponsor and cannot be communicated in any case

to a third party without the written agreement of the investigator.

Any publication or communication (oral or written) will be decided from a common agreement between the investigators and will respect the international recommendations: "Uniforms Requirements for Manuscripts Submitted to Biomedical Journals" (http://www.cma.ca/publications/mwc/uniform.htm): notably, an authorship will be proposed to each clinical center participating in the study and to each member of the steering committee according to his/her actual participation.

### Organization and responsibility

The Research Committee is responsible for developing study protocol, auditing patient eligibility and guiding interpretation of informed consent. It is also responsible for collection of complication reports, guiding diagnosis and treatment of complications and emergency intervention for serious complications, as well as approving the content and distribution of all publications related to the study.
